CCNES³⁹: The Coping with Children's Negative Emotions Scale is a self-report assessment which presents parent(s)/caregiver(s) with hypothetical scenarios in which their child is upset or angry (e.g. My child falls off their bike and breaks it, then gets upset and cries). Each scenario provides 6 possible responses to the child's distress and the parent(s)/caregiver(s) are asked to rate their likelihood of utilizing that response. Each response represents a different way of responding to a child's distress. It will be completed by the parent(s)/caregiver(s) of the child at pre- and post-test, and follow up.

Covariates

Prior to treatment, demographic information (e.g. child's age, sex, gender identity, ethnicity, language) will be provided by the child's parent(s)/caregiver(s). Demographic information is important for data analysis purposes and will allow us to identify any different patterns of treatment responses in different groups (e.g. treatment response in male children compared to treatment response in female children). Parents will report on their country of birth and their child's country of birth, as parents and children born outside of Canada often face immigration difficulties, cultural adjustment issues, and language barriers. Additionally, this allows us to evaluate the representativeness of our sample compared to the Canadian population. Information will be collected from the participants' health record on the number of sessions attended, and will be included as a control variable.

The parent(s)/caregiver(s) and child will report on the child's pubertal development, as indicated by the Tanner Stages Assessment⁴⁰. Information on pubertal development is needed because puberty can influence the physiological measures of emotion regulation being used in this study (e.g., heart rate variability). Parent(s)/caregiver(s) will report on their child's medication status pre- and post-test, at follow up, and quarterly during the course of treatment. To assess for satisfaction with treatment, parent(s)/caregiver(s) will complete the Youth Services Satisfaction Survey for Families⁴¹⁰.

At the post-test assessment, families in to the usual care condition will complete the Service Access Form to report any external services (e.g. couples therapy, psychoeducational assessment) they accessed while on the waitlist for usual care, or participating in usual care. It is common for families to be waiting for treatment from multiple services, or to seek private therapy while they are on our clinic's waitlist. This which will allow us to evaluate any pre-post change that may be due to those services. Families in the intervention condition will report on their access and use of external services at their 1-year follow up assessment.

Physiological Measures

Heart rate variability (HRV) and skin conductance level (SCL) will be measured using the widely used, non-invasive, compact mobile testing unit from *BIPAC*. This unit consists of two transmitter modules and a transducer (attached to two nylon belts and electrodes) that transmits physiological data to the BioNomadix Logger (BN-Logger), which is a battery-operated, wearable physiological recording platform capable of digitally storing signals for long periods of time. The comfortable system will be worn by the child as a bracelet and two belts for duration of the Trier Social Stress Test, the Pinata Task, Cognitive Reappraisal Task and Parent-Child Interaction.

MATCH Treatment

The intervention arm of this project will consist of a transdiagnostic psychotherapy treatment: *The Modular Approach to Therapy for Children with Anxiety, Depression, Trauma, or Conduct Problems (MATCH-ADTC)*⁴².

Two randomized effectiveness trials have demonstrated MATCH's effectiveness against usual care and standard treatment protocols (Cohen's d s from .47 to .55)⁴³⁻⁴⁴. MATCH draws from various domains of evidence-based treatment and consists of 33 treatment modules. There are several core module sequences for problem areas such as depression, anxiety, trauma, or disruptive behaviour and a clinician can utilize these sequences based on the primary concern for the individual. MATCH treatment usually ranges from 4 – 6 months, but the duration is flexible and dependent on the individual's needs. If an individual reports additional stressors or comorbid conditions, the clinician can modify the sequence of the modules to address these comorbidities. For example, if a child has been referred for the treatment of conduct problems, the clinician may utilize behavioural parent training, rewards, and time outs. If the child were to further report depressive symptoms, the clinician could incorporate modules from the depression pathway, such as problem solving and cognitive restructuring. MATCH treatment is flexible and can be tailored for each individual, so it is highly effective⁴⁵.

Clinicians administering MATCH-ADTC treatment will be asked to complete a Therapist Background Questionnaire⁴⁶, which asks about their training, educational background, and experience with child psychotherapy. They will have regular team meetings with the principal investigators ([name], [name], [name]) to discuss the implementation of the MATCH treatment program. These consultation meetings – which will not entail clinical supervision – are to support the implementation of MATCH with high fidelity. Brief consultation notes will be documented. All information shared at these meetings will be de-identified and personal health information will only be discussed on an as needed basis (e.g. age, sex, mental health concerns). To establish treatment alliance, adherence, and fidelity, therapy sessions will be audio recorded. A randomly selected 20% of the sessions will be coded for fidelity using the Therapist Integrity in Evidence Based Interventions and Therapy Process Observational Coding System – Alliance Scale⁴⁷. Clinicians will complete weekly session notes and fidelity checks, and at discharge of each MATCH-ADTC client, clinicians will complete the *Therapist Satisfaction Index*⁴⁸.

Control Group

Previous studies involving randomized waitlist controlled studies have established that MATCH-ADTC treatment is more effective than usual care. The justification of the control arm in this study is to allow us to evaluate the changes in biobehavioural regulation as a consequence of MATCH-ADTC treatment. The waitlist control exists to support our hypothesis that changes in emotion regulation are not merely due to the passage of time or normal emotional/psychological development in children.

The control arm of this project will consist of a no-treatment, waitlisted group. Participants in the waitlist condition will remain on the waitlist for standard usual care, and the estimated wait time is approximately 4-9 months. While in the waitlist control arm, participants are required to complete 75% of the weekly measures and attend both the quarterly (3-month) and the post-test study visit. If participants decide not to continue with the study, or they are lost to follow-up, they will be considered a drop-out in the Big Feelings Study, but their referral will remain open for usual care and they will remain on the clinic waitlist. Upon completion of the post-assessment, participants in the waitlist condition will be offered a bridging treatment (usually MATCH-ADTC treatment) until their usual care standard treatment spot becomes available, at which point they can decide whether they would like to continue with the bridging treatment or move to the standard care. Therefore, participants assigned to the control arm will also receive high quality, evidence-based treatment.

Compensation

Children and their parent(s)/caregiver(s) will be compensated for their participation. They will be provided with gift cards at each study visit and for completion of the weekly surveys. If participants are only able to complete the questionnaires, they still receive a portion of honorarium (see table, where the amount for “questionnaires” indicate how much participants can receive as honorarium for partial completion).

	Pre-Test Visit	Weekly Surveys	Quarterly Visit(s)	Post-Test Visit	
Parent	\$30 questionnaires only \$40 both questionnaires and in person visits	\$2 per survey \$5 bonus for every 5 completed	\$30 questionnaires only \$40 both questionnaires and in person visits	\$30 questionnaires only \$60 both questionnaires and in person visits	
Child	\$10 questionnaires only \$15 both questionnaires and in person visits	\$2 per survey \$5 bonus for every 5 completed	\$10 questionnaires only \$15 both questionnaires and in person visits	\$10 questionnaires only \$25 both questionnaires and in person visits	

Risks

There are minimal risks for participation in this study. The physiological measures (heart rate and skin conductance) are collected using a widely used, non-invasive, compact mobile testing unit that is worn like a bracelet and two belts attached to electrodes. Children may feel mild discomfort from the electrodes attached to the skin, and taking the electrodes off may feel like taking a “Band-Aid” which might be uncomfortable for some children.

However, parent(s)/caregiver(s) and children are shown all equipment and are encouraged to try putting on and peeling off the electrodes from the back of their hand prior to outfitting the child with

the equipment. If either the parent(s)/caregiver(s) or the child are not comfortable with the equipment and electrodes, they can choose to remove it at any time (as addressed in both the consent and assent process).

The assessment measures are validated and reliable, and have previously been used in large-scale studies. The only identifiable risk is that participants may find some of the questions to be difficult to discuss and stress inducing, such as questions about trauma. Participants can decline specific questions or questionnaires if they would prefer not to answer.

Benefits

Participation in this study has several potential benefits for the participants. If they are assigned to the MATCH-ADTC condition, they will receive an evidence-based treatment that has been shown to be highly effective. Additionally, there will be weekly check-ins and regular assessments with the waitlisted participants, which is not usually provided for clients on the waitlist.

Data Analysis

Preliminary analyses will test for significant differences in demographic factors between the MATCH and waitlist groups; significant factors will be covaried in our models. In the unlikely event that medication discrepancies are discovered between the two treatment groups, we will equate the groups by imposing propensity scores-based weighting in the analysis. An exploratory factor analysis (EFA) will examine whether the emotion regulation variables load onto a broad latent construct. Variables that do not load on the same factor will be examined independently within our mediation models. Latent Growth Curve (LGC) mediation modeling, which will account for the nested structure of the data as well as potentially unequally spaced time points, will test whether improvements in emotion regulation mediate improvements in symptoms as a result of MATCH treatment. We will conduct two types of mediation analyses corresponding to our operationalization of treatment response – pre-post change and trajectory of change. First, emotion regulation (latent biobehavioural regulation factor(s) from the EFA) will be modeled as a latent change from baseline to the 3-month quarterly assessment, and symptom change (CBCL/YSR internalizing and externalizing scores) will be modeled as a latent change from baseline to the post assessment. Our predictor will be specified as MATCH vs. Waitlist to ensure we can derive conclusions about the impact of MATCH on emotion regulation and symptoms. To test the mediated effect, we will apply the recommended bootstrap-based product of coefficients, which will yield bias-corrected 95% CIs based on the recommended asymmetric CI method. Second, to understand trajectories of change during MATCH treatment, we will apply LGC modeling to examine latent slopes of change in emotion regulation (weekly CADS) and symptoms (weekly BFS) and explore the temporal relations between the two trajectories. This will allow us to understand the temporal order and bi-directionality of changes in regulation and symptoms. In both modeling approaches, we will co-vary child age, gender/sex, medication use, puberty status, ethnicity, and treatment fidelity. We will apply an intent-to-treat approach and full information maximum likelihood estimation to account for potential bias caused by missing data.

In Aim 2, we will use machine learning techniques to uncover associations between biobehavioural indicators of emotion regulation (i.e., parent- and child-report questionnaires, performance on behavioural and cognitive tasks, physiological reactivity, and family factors) and treatment response (i.e., trajectory of symptom change). Association rule mining will identify patterns of observed values in our emotion regulation indicators that are significantly related to treatment response by looking for frequencies of co-occurrence of the specific indicator and response values that are significantly different than that expected under random chance. This is calculated by the Haberman residual and

provides a z-score indicating the likelihood of random occurrence of an observation. Together, these significant co-occurrences, or “patterns”, (i.e., those not occurring due to chance or noise) will provide a model of the data that can be used to predict treatment response trajectories. We will follow recommended nested cross-validation which validates patterns by examining the pattern discovery across a set of cross-validation trials. Participant data will be allocated in round-robin fashion into N sets. We will use 10-fold cross-validation such that a “fold” is created by using one set only for testing, and dividing the remaining between training and parameter validation. This allows unseen validation data to determine the efficacy of the discovered patterns obtained from the “training” sets and allows detection of overfitting using the validation sets. This process is then repeated whereby each fold is used only once for model testing, which will also allow us to assess the stability of the patterns discovered across the collection of training and validation exercises. Overfitting of the process is properly managed through this cross-validation strategy. In addition, we have addressed overfitting by employing association mining (versus, for example, convolutional neural networks) because it is associated with a much lower risk of overfitting (Hamilton-Wright & Stashuk, 2009) and provides a simple statistical measure of rule significance. To establish the power of these patterns, we will use information theory to score each one, describing how much support each pattern has within the overall distribution of the data. This allows us to distinguish patterns based on richly described regions of the data distribution from those with sparse support. The result is a confidence value associated with assertions made about treatment response using the patterns, indicating whether there is high confidence (based on well characterized regions of the data) or poor confidence (based on rare or conflicting regions of the data). Altogether, significant and meaningful rules and associated confidences are assembled into a rule-based framework that will allow characterizations (i.e., predictions) to be made, in new cases, describing the likely treatment response trajectory based on emotion regulation indicators. As one example, the algorithm could reveal that when child arousal (i.e., skin conductance level) is above a certain threshold, treatment response is slow, and that the framework’s confidence in this characterization is 90%. Such a result would suggest that child arousal, when above a certain threshold, is a key regulation component in treatment response, that there is a high amount of evidence within the system for this characterization, and that it would be worthwhile to consider when tailoring psychotherapy. The resulting set of significant and meaningful association rules, or algorithms, will be applied to a predictor system,⁸⁰ which will form the basis of bidirectional and iterative conversations with KT users and partners about applying the algorithms to a clinical decision-making framework.

Knowledge Translation

In Aim 3, we will translate findings from Aim 2 by engaging clinical leaders in the CAMH CYEAP. Once data have been collected, discussions will involve reviewing and refining the rule-based algorithms from our machine learning analyses. Through a bidirectional and iterative process, we will develop a clinical decision-making framework that applies these rules to predict treatment trajectories. We will also engage with community stakeholders, particularly families with lived experience as caregivers for children with mental health difficulties. We will also engage in broader information dissemination and KT uptake of our findings to academic (e.g., international conferences, peer-reviewed publications) as well as clinical (e.g., clinicians, trainees) and community audiences (e.g., family partners). One expected outcome of our research will be knowledge gained about transdiagnostic mechanisms of change in child psychotherapy for emotional and behavioural problems. This knowledge will be disseminated to clinicians and trainees at CYEAP and CPS through invited talks, trainings, newsletters, and web platforms. We will also leverage existing knowledge dissemination activities and outlets such as monthly rounds that are well-attended by both clinicians and researchers, newsletters, and the

References

1. Fergusson, D. M., & Woodward, L. J. (2002). Mental health, educational, and social role outcomes of adolescents with depression. *Archives of General Psychiatry*, 59, 225–231
2. Masten, A. S., Roisman, G. I., Long, J. D., Burt, K. B., Obradovic', J. R., Boelcke-Stennes, K., et al. (2005). Developmental cascades: Linking academic achievement and externalizing and internalizing symptoms over 20 years. *Developmental Psychology*, 41, 733–746.
3. Marchette, L.K., [name], K., Hersh, J., MacPherson, H.A., Santucci, L., Weisz, J.R. (2019). Community Mental Health Settings. In T.H. Ollendick, S.W. White, & B.A. White (Eds.) *The Oxford Handbook of Clinical Child and Adolescent Psychology*.
4. Weisz, J. R., Kuppens, S., Ng, M. Y., Eckshtain, D., Ugueto, A. M.,... & Weersing, V. R. (2017). What five decades of research tells us about the effects of youth psychological therapy: a multilevel metaanalysis and implications for science and practice. *American Psychologist*, 72, 79-117.

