Study Design

This project will have several components, which we anticipate will unfold over the course of 5 years. The first step of the process will be training research and clinical staff; practicum students, psychology residents, and staff clinicians at CAMH on administering the Modular Approach to Therapy for Children with Anxiety, Depression, Trauma, and Conduct Problems (MATCH-ADTC) treatment. The study investigators will be primarily involved in training clinical staff on MATCH-ADTC treatment. They will not be directly involved in administering care, but they will be responsible for supervising practicum students and residents administering care. These students are clinical trainees in a doctoral program for clinical psychology, supervised by registered psychologists at CAMH (e.g., [name], [name]). These students have previously completed coursework and training in therapeutic methods. When matching clients to students, we will consider the expected length of treatment in relation to the length of their practicum or residency. Most practicums and residencies range from 9 months to 12 months, which will provide ample time to complete most courses of treatment. In the case that a student is unable to complete a course of treatment for a client, we will ensure continuity of care as is standard within our clinical services. There would be a plan for a warm transfer, where another trainee or clinician would continue treatment.

Children and their parent(s)/caregiver(s) will be recruited on an ongoing basis from two outpatient children's mental health clinics (CAMH and University of Guelph). Senior research staff will screen families, enroll them in the study, and conduct pre-treatment assessments. After enrolment and collection of initial measures, participants will be randomly assigned to the intervention arm or the waitlist control arm. We anticipate that the duration of both MATCH-ADTC treatment and the waitlist will range between 4 – 6 months, which is similar to the usual wait times for services at both clinics.

During this period, participants in both arms will complete brief weekly measures, which consist of very brief symptom scales. Participants will be required to complete quarterly assessments (approximately 3 months following their initial assessment), which will consist of symptom scales, medication tracking, clinical interviews, experimental tasks and physiological measures.

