Following the intervention or waitlist period, our team will conduct post- assessments. The post-assessments will allow us to analyze any changes in biobehavioural regulation and compare the differences between the intervention and control arms. Participants in the control arm will complete the post assessment approximately 4-6 months after their initial assessment, or prior to them being picked up off the waitlist for treatment in the clinic. . As screening and enrolment are ongoing, we will consistently clean data and engage in quality assurance procedures to ensure our methods are rigorous and meet scientific standards.

Participant Recruitment

Children will be recruited from the Child, Youth, and Emerging Adult Program (CYEAP) at CAMH and at the Maplewoods Centre for Family Therapy and Child Psychology at the University of Guelph.

Approximately 250 families (children aged 8 – 15, and their parent(s)/caregiver(s)), seeking psychotherapy for child anxiety, depression or disruptive behaviour will be recruited for this study. Families recruited from CAMH will have been referred to the Better Behaviours Service or Mood & Anxiety Clinic, or will be on the psychiatric assessment waitlist. Many families on the waitlist wait over a year for psychiatric evaluation, and many do not need or benefit from an assessment because they have been referred specifically for psychosocial treatment, and may already have a diagnosis and prescribed medication. To reduce the wait times for families and reduce the assessment burden, clinicians will screen families before their psychiatric assessment to identify children who may benefit from directly receiving psychosocial treatment without needing a psychiatric assessment first. These families will be contacted and asked to complete a short clinical screening (i.e. reason for referral) and approached to participate in research if the clinical team thinks the family would be a good fit. This process follows a similar procedure previously approved for use in our clinic (REB #018/2022).

Initial Research Contact

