If the clinical-research team member is the first point of contact discussing research in detail, clients are given the opportunity to participate in a clinical trial, learn about the potential benefits of treatment, as well as the risks and alternatives. This process follows a core GCP principle of *respect for persons and beneficence* in that all clients are given the opportunity to choose if they want to participate in a clinical trial or not after receiving detailed information about the potential risks, benefits, and alternatives to participation. Efforts are taken to provide all possible options and alternatives to reduce any perceived or actual pressure on clients. Additionally, our consent form is structured in a way that participants can decline aspects of the study and still participate in others and receive treatment. If families choose not to participate in research, they are provided with the standard of care at the BBS and MAC, which includes assessment and treatment services as usual.

Sample Size

A Monte-Carlo simulation study with 1000 replications, moderate treatment effect ($d = 0.5$) α of 0.05 and β of 0.2, and 25% as the proportion mediated resulted in a required sample size of $N = 168$. We anticipate an attrition rate for both the intervention arm and the waitlist arm to be 20%, so we increased our sample size to 202. The Child, Youth and Family Services at CAMH and Maplewoods Centre at Guelph receive approximately 400 new child referrals per year within the age range and diagnostic criteria, so this target is quite feasible.

Clinical Records

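### The 20% attrition allowance multiplies where it should divide: 202 enrolled leaves about 162, not the required 168; the correct figure is 210

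*Protocol*

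**What the plan says.** The Sample Size section of the protocol reports a Monte-Carlo simulation with 1000 replications, a treatment effect of d = 0.5, α of 0.05, β of 0.2, and "25% as the proportion mediated resulted in a required sample size of" 168. It then expects attrition in both the intervention and the waitlist arm "to be 20%, so we increased our sample size to 202". The next sentence treats 202 as the target and judges it feasible against about 400 new referrals per year.

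Two other places bear on the point:

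- Participant Recruitment gives a different number, "Approximately 250 families", and does not tie it to 168, to 20% or to 202. Study Design says families are recruited from the two clinics and then: "Senior research staff will screen families, enroll them in the study". Randomisation follows.
- Data Analysis plans an intent-to-treat analysis with "full information maximum likelihood estimation to account for potential bias caused by missing data".

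**The concern.** An attrition rate applies to the people who enter the trial, so the number to enrol is the requirement divided by the retained fraction. Adding 20% of the requirement is a different calculation and always gives a smaller number. The stated 202 looks like the second calculation. If so, the protocol's sample size does not meet its own requirement under its own attrition assumption, and the planned 80% power is not quite reached.

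The unexplained 250 adds to the difficulty. A reader cannot tell whether the trial means to randomise 202, 250 or some other number, and so cannot tell whether the shortfall will occur in practice.

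**Working it through.** **Inputs, all from the Sample Size section unless noted.** Required N = 168; attrition = 20% in both arms; stated sample size = 202; β = 0.2, that is, 80% power; d = 0.5; proportion mediated = 25%; 1000 replications. Participant Recruitment: about 250 families. The path coefficients behind 168 are not given, so 168 is taken as stated and not re-derived.

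**1. Reproduce the stated figure.** N × (1 + attrition) = 168 × 1.20 = 201.6, rounded up to 202. This matches.

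**2. What 202 delivers.** 202 × (1 − 0.20) = 161.6. Shortfall: 168 − 161.6 = 6.4, that is, 6 if 162 remain and 7 if 161 remain.

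**3. What is needed.** N/(1 − attrition) = 168/0.80 = 210. Check: 210 × 0.80 = 168. Difference from the stated figure: 210 − 202 = 8, and 8/202 = 4.0%.

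**4. Attrition that 202 can absorb.** 1 − 168/202 = 16.8%, below the 20% assumed.

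**5. Power, by simple scaling.** Assume that power is exactly 80% at 168, that the test is two-sided at 5% (the protocol does not say), and that the noncentrality grows with √N. At 168 the noncentrality is 1.960 + 0.842 = 2.802.

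- At 161.6: Φ(2.802 × √(161.6/168) − 1.960) = 0.785, a loss of about 1.5 points.
- At 200, which is 250 × 0.80: Φ(2.802 × √(200/168) − 1.960) = 0.864.

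**6. Sensitivity of the loss.** A mediated effect has two paths, so a joint-significance approximation is a useful second look. Assume an indirect effect ab = 0.25 × 0.5 = 0.125, with z-values a√N/2 for treatment to mediator and b√N for mediator to outcome. Power is the product of the two path powers.

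| Assumed a | Power at 168 | Power at 161.6 | Loss (points, from unrounded values) |
|---|---|---|---|
| 0.35 | 0.619 | 0.601 | 1.7 |
| 0.40 | 0.723 | 0.704 | 1.9 |
| 0.50 | 0.810 | 0.789 | 2.0 |
| 0.60 | 0.750 | 0.730 | 1.9 |
| 0.70 | 0.635 | 0.618 | 1.8 |

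The level of power depends strongly on how the effect splits between the paths, so this table neither confirms nor disputes 168. The loss is stable at about 1.7 to 2.0 points.

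**7. Precision of the base figure.** The Monte Carlo standard error at 80% power with 1000 replications is √(0.80 × 0.20/1000) = 1.26 points, so the 95% margin is about ±2.5 points.

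**The case against.** The arithmetic itself is hard to contest. The case on the other side concerns how much it matters.

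- **The effect is within simulation noise.** A loss of 1.5 to 2 points is smaller than the ±2.5-point margin on the simulation that produced 168. This is true, and it limits the importance of the point. But simulation error can go either way, whereas this slip always enrols too few.
- **The 250 families may cover it.** If 250 are randomised, 200 remain after 20% attrition, well above 168. This stands as a possibility. Recruitment comes before screening and enrolment in Study Design, so 250 may be a count further upstream, and the Sample Size section names 202 as the target. The figure is therefore one to explain. It is neither a proven rescue nor a proven contradiction.
- **Drop-outs still contribute.** Full information maximum likelihood uses partial records. A child lost after the 3-month visit still informs the treatment-to-mediator path, so the power loss above is an upper bound under its assumptions. Recovery has limits, however: after withdrawal no visits are scheduled and no measures are sent (Consent and Assent), and a child lost before 3 months has neither the follow-up mediator visit nor the post-assessment. In any case the protocol chose to inflate for attrition, and the inflation should do what it sets out to do.
- **A power figure obtained by scaling should not be printed as the trial's own.** This is fair. A figure for about 162 is best confirmed by re-running the sponsor's simulation.

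**Conclusion.** The concern holds. The figure of 202 is wrong as written: it comes from multiplying by 1.20, and under the protocol's own 20% attrition it leaves about 162 instead of 168. The correct allowance gives 210. This conclusion needs no assumption beyond the protocol's own numbers.

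The consequence is modest. If 202 is the number randomised and only completers count, power falls by roughly 1.5 to 2 points, to about 78.5% under √N scaling from an exact 80% at 168. With partial data retained, the loss should be no larger than that. Whether the trial ends up short in practice depends on what 250 counts, which the protocol does not say. The point should be corrected, but it does not threaten the design.

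**What to change.** In the Sample Size section, do one of the following:

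- replace 202 with 210, showing 168/0.80; or
- keep 202 and state that about 162 are expected to remain, with the correspondingly reduced power (about 78% under √N scaling, ideally confirmed by re-running the simulation at that number).

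In Participant Recruitment, state whether the 250 families are those approached, consented or randomised. If 250 is the number randomised, give it as the target in the Sample Size section, together with the 200 expected to remain after attrition.

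The cost is one corrected figure and one clarifying sentence. Enrolment rises by at most 8 families, about 4%, against roughly 400 referrals per year in the stated age and diagnostic range; exclusions, consent and assent will reduce that pool.
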